# 2 SYNOPSIS

Title of Study	Prospective, evaluator-blind, multicenter study to assess the safety and effectiveness of treatment with the Octave System for improving lines and wrinkles of the décolleté		
Study Identifier	M960101003		
Number of Sites and Countries	This study will be conducted at up to 10 investigational sites in the United States.		
Investigational Medical Device	Octave System		
Indication	Improvement in lines and wrinkles of the décolleté		
Objective	To demonstrate the safety and effectiveness of the Octave System for improving lines and wrinkles of the décolleté.		
Effectiveness Evaluation	
 
Primary endpoint
 
Proportion of treated subjects with improvement in lines and wrinkles of the décolleté by comparing photographs taken at Day 90 (post-treatment) with baseline (pre-treatment) photographs.
 
Improvement is concluded if at least two of three independent, blinded evaluators assess the Day 90 standardized, photographic images as improved compared to baseline photographic images.
 
Secondary endpoint
 
Proportion of treated subjects with improvement in lines and wrinkles of the décolleté by comparing photographs taken at Day 180 (post-treatment) with baseline (pre-treatment) photographs.
 
		
Safety Evaluation	Secondary endpoint     Incidence of treatment-emergent adverse events (TEAEs), related to Octave-Ultherapy treatment, as reported throughout the study.		
Study Design Overview and Methodology	This is a 180-day, prospective, evaluator-blind, multicenter, staged, confirmatory study designed to evaluate the safety and effectiveness of the Octave System for improving lines and wrinkles of the décolleté.  All enrolled healthy, adult female subjects with moderate to severe fine lines, wrinkles, laxity, and crepiness of the décolleté will receive a single Octave-Ultherapy treatment of the décolleté tissue with two transducers at energy level 4  and one transducer at energy level 3  Subjects will be followed for 180 days, and photographs will be taken at baseline, Day 90, and Day 180.  For the primary endpoint, improvement in the appearance of the décolleté will be determined by a blinded, independent assessment of photographs at 90 days post-treatment compared to baseline. The same photograph		

	100 1		
	comparison will be made at 180 days post-treatment for the secondary endpoint. To reduce potential bias associated with evaluating only treated-subject photographs, images of untreated individuals, collected at two time points, will also be included for blinded, independent photographic review.		
	Study subjects will have approximately 4 in-office study visits, including screening, baseline/treatment, a Day 90 ( $\pm$ 7 days) post-treatment visit, and a Day 180 ( $\pm$ 14 days) post-treatment visit. Follow-up telephone calls will occur at 3 days ( $\pm$ 1 day), 14 days ( $\pm$ 3 days), 28 days ( $\pm$ 3 days), 120 days ( $\pm$ 7 days), and 150 days ( $\pm$ 7 days) after Octave-Ultherapy treatment.		
	Expected study duration is approximately 8 months from screening of the first subject until final follow-up of the last subject. In Stage 1, an initial cohort of 10 subjects will be enrolled, safety data will be assessed up to Week 2, and subjects will participate until the Stage 1 study end at Day 90. In Stage 2, all enrolled subjects will participate until study end at Day 90 or Day 180 if reconsented for extended participation. The planned duration of participation for individual subjects is up to 30 weeks, including up to 21 days for screening, 1 day for treatment, and 90 or 180 days for follow-up.		
Number of Study Subjects	Approximately 113 subjects are planned for screening to allow for 90 enrolled/treated subjects and 80 evaluable subjects in this study. In Stage 1, 10 subjects will be enrolled, while all other subjects will be enrolled in Stage 2.		
	Key inclusion criteria are as follows:		
	Healthy female aged 35 to 65 years at the time of screening.		
	
 
Moderate to severe fine lines, wrinkles, laxity, and crepiness of the décolleté that is amenable to improvement with non-invasive intervention and is not severe enough for surgical intervention.
 
		
Main Inclusion/	Key exclusion criteria are as follows:		
Exclusion Criteria	
 
Presence of an active systemic or local skin disease that may affect wound healing.
 
		
	
 
Scarring in area(s) to be treated.
 
		
	
 
Active implants (e.g., pacemakers or defibrillators), ports, or metallic implants in area(s) to be treated.
 
		
	
 
Breast implants or is planning to receive breast implants during the study.
 
		
	
 
Inability to take pre-treatment medications due to a pre-existing condition, medication allergy, or medical issue that, at the discretion of the treating investigator, is contraindicated.
 
		

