#### 5.2 Informed Consent

Verbal and written informed consent must be obtained from every subject prior to the initiation of any screening or study procedures. The investigator will follow a standard process for obtaining consent that complies with all applicable regulatory requirements. If applicable, a certified, local-language translation of the informed consent form (ICF) will be provided.

If the ICF is amended during the study, the investigator must follow all applicable regulatory requirements pertaining to approval of the amended ICF by the IEC/IRB and use of the amended form. Ongoing subjects will be required to re-confirm consent by signing the amended form.

The original and any amended signed and dated ICF(s) must be retained at the study site; a copy of the signed and dated ICF(s) must be given to the subject.

During the study, the subject will be informed if information becomes available that may be relevant to the subject's willingness to continue participation in the study. Each ICF will include contact information (with a phone number) the subject should use to communicate any medical concerns 24 hours a day. The subject, however, is free to withdraw consent at any time and for any reason, whether expressed or not.

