#### 9 STUDY POPULATION AND RESTRICTIONS

#### 9.1 Number of Subjects and Sites

Approximately 80 evaluable subjects, who complete the full Ultherapy treatment session using the Octave System, are planned for this study. Assuming a screen failure rate of 20%, approximately 113 subjects will be screened; assuming attrition of 10 subjects, approximately 90 subjects are planned for enrollment/treatment. All subjects will sign and date the ICF before any study-related procedures are undertaken.

In Stage 1, 10 subjects will be enrolled at a minimum of two investigational sites (maximum: 6 sites) in the United States, while all other subjects will be enrolled in Stage 2. Number of investigational sites will not exceed ten in total. During Stage 1, Week 2 safety data for the first 10 treated subjects will be evaluated. All 10 subjects enrolled in Stage 1 will participate until Stage 1 study end at Day 90. In Stage 2, all other enrolled subjects will participate for at least 90 days ( $\pm$  7 days), with a maximum duration of 180 days ( $\pm$  14 days) if reconsented for extended participation. Females of all FST are eligible for study participation. In addition, approximately 10% of the enrolled subjects will be categorized as FST IV, V, or VI, and of which 5% will be categorized as FST V or VI.

Subjects who are enrolled and who do not complete the study will not be replaced. Furthermore, the secondary effectiveness endpoin at Day 180 will only be assessed among subjects who reconsent at their Day 90 visit for extended study participation to Day 180.

Photographs of approximately 30 untreated individuals, who meet selected appearance criteria (Section 11.2.1.1.1), will be collected at two different time points, between 1 day and 1 week apart; these photographs will be subsequently paired for evaluation by the independent, blinded evaluators.

To confirm the presence of appropriate anatomy at the intended depth of treatment (see Inclusion Criterion #3 in Section 9.2.1), the treating investigator will use the Octave System's supplemental imaging mode to visualize the dermal and subdermal layers of tissue. For example, subjects with bone, rather than soft tissue, at the intended treatment depth would be considered screen failures and would not be eligible for enrollment. [16]

Additional information regarding subject enrollment is provided within the sample size justification (Section 13.1).

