## 10.4 Blinding Procedures

In this non-comparative study, investigators and subjects will not be blinded to treatment. Three independent, photographic evaluators will be blinded for the primary effectiveness endpoint as described in Section 8.1.

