## 11 STUDY PROCEDURES

#### 11.1 Visit Schedule

The investigation activities and visit schedule are detailed in the Schedule of Events

The purpose of the screening visit (Visit 1) is to determine subject eligibility for study participation and must be completed no more than 21 days prior to Day 1 (Visit 2). Informed consent is to be obtained at the screening visit, and the reviewing/recording of AEs begins upon ICF signature. Subject demographics, including FST should be recorded in the eCRF, and a subject-reported medical history is acceptable.

Note: Additionally, for each site, approximately the first four to five subjects with moderate to severe fine lines, wrinkles, laxity, and crepiness of the décolleté, as enrolled by the investigator, will be confirmed for study-appropriate lines and wrinkles of the décolleté via an independent photographic reviewer.

In addition to the activities listed in the Schedule of Events

- At Visit 2 (Day 1), prior to performing the investigator's skin examination, the subject must wash the treatment area to remove any moisturizers/emollients, makeup, bronzing agents, etc. on the neck/décolleté region, if necessary.
- study personnel should schedule follow-up phone call(s) and Visit 3.
- At Visit 3, subjects will be requested to reconsent for extended study participation to 180 days. If reconsented, study personnel should schedule follow-up Day 120 and Day 150 phone call(s) and Visit 4.
- All required subject-related, pre-treatment procedures and assessments should be completed before the administration of oral or IM pain medication (Section 10.5.1.2).
- After administration of the pain medication, study personnel should verify all study-specific treatment settings on the Octave System and prepare study-specific materials needed for treatment (e.g., ultrasound gel). Study personnel should prepare inhaled nitrous oxide/oxygen mixture for potential use, if available.

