6.1.2 Secondary Effectiveness Endpoint

The secondary endpoint will only be assessed among subjects reconsented for extended study participation.

The secondary endpoint of the study is the proportion of treated subjects with improvement in lines and wrinkles of the décolleté by comparing photographs taken at Day 180 (post-treatment) with baseline (pre-treatment) photographs.

Each independent evaluator will assess “Improvement”, “No Improvement” or “Cannot Evaluate” between Photograph 1 (baseline) and Photograph 2 (post-baseline). Photograph 1 will be identified, and the independent evaluators will be blinded to the random distribution of treated versus untreated status of the comparator Photograph 2 (i.e., Day 180 post-treatment among treated subjects or post-baseline for untreated individuals). If photographs are declared as not assessable during the Day 180 assessment session, the evaluators will be instructed to rate the corresponding Photograph 2 as “Cannot Evaluate”.

Improvement will be declared if at least two blinded evaluators indicate “Improvement” for the comparator photograph. In case at least two evaluators declare a photograph as not assessable (i.e., “Cannot Evaluate” is ticked), the corresponding improvement score over all evaluators will be set to missing for the secondary analysis. In case one evaluator rates a photograph as “Cannot Evaluate” and the other two evaluators disagree, the overall improvement score will be set to “No Improvement”.

[figure not shown]
The proportion of subjects fulfilling the secondary endpoint will be described by frequency statistics for the ITT subset, including the one-sided 95% Wilson CI.

Missing data, including a missing secondary endpoint assessment in subjects with unacceptable, not assessable or missing photographs at baseline or Day 180, will be imputed by multiple imputation. In case of complete data, no multiple imputation will be performed and the primary analysis is based on complete data for the ITT.

Imputation is done 50 times using a fully conditional specification logistic regression method, as implemented in SAS PROC MI with statement FCS LOGISTIC, and will use the investigational site and the baseline characteristics age and BMI as informing variables. Point estimate and Wilson CI will be calculated with methods as described in Section 6.1.1.1. For implementation, SAS code similar to the statements for the primary endpoint will be used.

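### Consent to Day 180 follow-up is sought only at the Day 90 visit, from unblinded subjects who can see their own skin, so entry to the Day 180 cohort can depend on perceived response

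*Protocol*

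**What the plan says.** **Length of follow-up.** The methodology part of the Protocol synopsis contains an unconditional sentence: "Subjects will be followed for 180 days, and photographs will be taken at baseline, Day 90, and Day 180". Further down, the same synopsis adds the condition: "In Stage 2, all enrolled subjects will participate until study end at Day 90 or Day 180 if reconsented for extended participation". Stage 1 is shorter by design (Protocol 9.1): "All 10 subjects enrolled in Stage 1 will participate until Stage 1 study end at Day 90".

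**When consent is asked.** Protocol 11.1: "At Visit 3, subjects will be requested to reconsent for extended study participation to 180 days". It does not limit the request to Stage 2 and does not place it before or after the skin examination and photographs of that visit.

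**Who is analysed at Day 180.** Protocol 9.1 states that the secondary effectiveness endpoint "will only be assessed among subjects who reconsent at their Day 90 visit for extended study participation to Day 180". SAP 6.1.2 agrees: "The secondary endpoint will only be assessed among subjects reconsented for extended study participation". The same SAP section also refers to the ITT subset and to multiple imputation of missing Day 180 results from site, age and BMI.

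**Blinding.** Protocol 10.4: "In this non-comparative study, investigators and subjects will not be blinded to treatment". Only the three photographic evaluators are blinded.

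**Consent amendments.** Protocol 5.2, on an amended form: "Ongoing subjects will be required to re-confirm consent by signing the amended form". Nothing there ties the signature to Visit 3.

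**The concern.** Membership of the Day 180 cohort is settled about 90 days after treatment, at the visit where the primary endpoint is measured, by a subject who knows she was treated and can look at her own skin. The request comes from a site that is also unblinded. If willingness to continue is related to how she thinks she has done, the reconsenters are not a representative sample of the treated Stage 2 subjects.

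At stake are the only secondary effectiveness endpoint, which would carry any statement about durability, and the adverse event data after Day 90, which come from the same self-selected group. The timing does not appear to be forced: Section 5.2 lets an amended form be signed earlier, and new subjects could be asked for the whole period at screening.

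**Working it through.** **1. The plan's own figures.** The documents give no expected reconsent rate, Day 180 rate or Day 180 sample size, so there is no Day 180 figure to reproduce. The primary design does reproduce. With 80 evaluable subjects the Wilson bound passes 50% from 48 responders, and the 65% rule needs 0.65 × 80 = 52. Exact binomial power for 52 or more at a true 70% is 86.3%, against the stated 85% or more. None of this depends on Day 180 reconsent.

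**2. Size of the pool.** About 90 enrolled less 10 in Stage 1 leaves at most about 80 Stage 2 subjects, or about 70 if all 10 planned losses fall in Stage 2. The percentages below do not depend on which figure is used.

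**3. Apparent rate among reconsenters.** Let t be the true Day 180 improvement rate, and a and b the reconsent rates of improved and non-improved subjects. Then

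apparent rate = t·a / (t·a + (1 − t)·b).

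All three inputs are assumptions. With t = 0.60:

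| a / b | Calculation | Apparent rate | Shift (points) | Reconsenters out of 80 |
|---|---|---|---|---|
| 80% / 70% | 0.48 / (0.48 + 0.28) | 63.2% | +3.2 | 60.8 |
| 90% / 60% | 0.54 / (0.54 + 0.24) | 69.2% | +9.2 | 62.4 |
| 70% / 80% | 0.42 / (0.42 + 0.32) | 56.8% | −3.2 | 59.2 |

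Equal reconsent gives no shift. The last row is the case where dissatisfied subjects are keener to stay.

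**4. Attenuation.** Step 3 ties reconsent directly to the Day 180 outcome, which does not yet exist when consent is asked. Suppose instead that Day 90 response drives reconsent and only partly predicts Day 180. Take 70% Day 90 responders (the protocol's planning value) and assume Day 180 improvement in 85% of Day 90 responders and 25% of non-responders. The true Day 180 rate is 0.70 × 0.85 + 0.30 × 0.25 = 67%. With reconsent of 90%/70% the apparent rate is (0.70 × 0.90 × 0.85 + 0.30 × 0.70 × 0.25) / (0.63 + 0.21) = 0.588 / 0.84 = 70.0%, a shift of +3.0 points. Direct dependence at the same 67% would give 0.603 / (0.603 + 0.231) = 72.3%, or +5.3 points. More extreme assumed rates under the partial model (90%/50% and 95%/40%) give 73.5% and 75.8%.

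**5. Why the imputation does not help.** If imputation covers only reconsenters with a missing rating, decliners stay out. If it covers decliners too, they receive roughly the reconsenters' rate for their site, age and BMI. In the 90%/60% row the decliners' true rate is (0.60 × 0.10) / (0.60 × 0.10 + 0.40 × 0.40) = 0.06 / 0.22 = 27%. A model in which site, age and BMI do not explain the selection would fill them in at about 69%. Day 90 response is not named in the visible imputation model.

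**6. What a worst-case analysis would show.** Counting all decliners as not improved gives t·a: 54% in the 90%/60% row, 48% for 80%/70% and 42% for 70%/80%. It is a lower bound, not an estimate.

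**The case against.** The strongest reply is that the restriction to reconsenters is stated openly, affects one descriptive secondary endpoint, and has an unknown effect. Much of this stands, and it rules out several stronger readings.

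- *That the synopsis contradicts the body.* A reader might infer this from the unconditional sentence. It is not so: the synopsis itself gives the reconsent condition and ends Stage 1 at Day 90. One loose sentence needs reconciling.
- *That the subject knows her result.* She can see her skin. No visible text gives her the evaluators' ratings, and the endpoint is their majority judgement.
- *That the bias is upward and large.* The documents give no direction. The reverse pattern lowers the rate, and partial prediction shrinks the shift.
- *That a failing rate could be lifted past 65%.* The 65% and 50% rules belong to the Day 90 primary endpoint. The visible text sets no success threshold for Day 180.

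A further reply is that SAP 6.1.2 promises sensitivity analyses similar to those for the primary endpoint, which include missing counted as no improvement. That would help only if decliners count as missing. With the endpoint assessed only among reconsenters, the SAP leaves this open.

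Finally, earlier consent does not remove the selection. Subjects can still withdraw, so some of it may return as dropout. Asking just before the Visit 3 photographs would change little, because the skin is already visible by then. The consent pages are not available, nor is it known how many subjects remain to be screened, so the reach of a screening-stage remedy is uncertain.

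**Conclusion.** The concern holds in limited form. Consent to Day 180 is requested at the Day 90 visit, from unblinded subjects, and the Day 180 endpoint is confined to those who agree. Entry can therefore depend on perceived response, and nothing in the visible text prevents or corrects that.

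The size is illustrative only. At a true 60% the apparent rate runs from about 57% to 69% across the three assumed patterns, and less far from 60% if Day 90 appearance is a weak guide to the Day 180 rating. Direction and magnitude rest wholly on assumed reconsent rates. The primary endpoint, its power and its error rate are untouched. This is a cheap improvement, not a flaw in the confirmatory analysis.

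**What to change.** 1. **Stage 2 subjects still to be screened:** include follow-up to Day 180 (the Day 120 and Day 150 calls and Visit 4) in the screening consent, keeping the right to withdraw at any time.
2. **Stage 2 subjects already enrolled:** present the extension form as early as possible and ahead of Visit 3, through the amended-consent process in Protocol 5.2.
3. **Wording:** change Protocol 9.1 and 11.1 to match, state in 11.1 whether Stage 1 subjects are excluded from the request, and reconcile the unconditional synopsis sentence with the rest of the synopsis and with 9.1 and 11.1.
4. **Subjects who could only be asked at Day 90:** report Day 90 response by reconsent status, and specify in SAP 6.1.2 a Day 180 sensitivity analysis that counts Stage 2 non-reconsenters as no improvement.

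The cost is revised consent and protocol wording, IRB approval of the form, and a short SAP addition. A few candidates may decline the longer commitment at screening. The change reduces the selection but does not eliminate it.

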# 4 LIST OF ABBREVIATIONS AND DEFINITIONS OF TERMS

Abbreviation	Definition
ADE	Adverse device effect
AE	Adverse event
ASADE	Anticipated serious adverse device effect
ATC	Anatomical Therapeutic Chemical class ification system of the World Health Organization
BL	Baseline
BMI	Body mass index
BRCA	BReast CAncer gene
CD	Compact disc
CFR	Code of Federal Regulations
CI	Confidence interval
COVID-19	Coronavirus dis ease 2019
CRO	Contract research organization
CSP	Clinical studyprotocol
DS	DeepSEE
DVD	Digital versatile disc
eCRF	Electronic case report form
EDC	Electronic data capture
EL	Energy level
FCS LOGISTIC	Fully conditional specification logistic regression method
FDA	Food and Drug Administration (US)
FST	Fitzpatrick skin type
GCP	Good Clinical Practice
GDPR	General Data Protection Regulation
HIPAA	Health Insurance Portability and Accountability Act of 1996 (US)
ICF	Informed consent form
ICH	International Conference on Harmonization of Technical Requirements for Registration of Pharmaceuticals for Human Use
ID	Investigational device (termus ed interchangeably with investigational medical device (IMD))
IEC	Independent ethics committee
IFU	Instructions for use

Abbreviation	Definition
IM	Intramus cular, as in treatment administration route
IMD	Investigational medical device (termus ed interchangeably with Investigational Device (ID))
IRB	Institutional Review Board
ISO	International Organization for Standardization (EN = English translation)
ITT	Intent to treat
MedDRA	Medical Dictionary for Regulatory Activities
N	Number of non-missing observations
NRS	Numerical Rating Scale
NSAIDs	Nonsteroidal anti-inflammatory drugs
OT	Octave Systemtransducer
РНІ	Protected health information
PO	Per os (Latin); used in medicine to describe treatment administration by oral route
PP	Per protocol
PT	Preferred term
SADE	Serious adverse device effect
SAE	Serious adverse event
SAP	Statistical analysis plan
SAS	Statistical Analysis Software®
Scr	Screening
SD	Standard deviation
SOC	Systemorgan class
SOP	Standard operating procedure
SP	Safety population
SPF	Sun protection factor
SSQ	Subject Satisfaction Questionnaire
TCP	Thermal coagulation point
TEAE	Treatment-emergent adverse event
TESAE	Treatment-emergents erious adverse event
UADE	Unanticipated adverse device effect
US	United States
UV	Ultraviolet

